4.4.4. Rationale for Open-label Design

Several options for control groups were considered in the design of Study 304. A placebo control was not considered appropriate for this PK study, which is designed to fulfill the obligations of the full extrapolation model. An active control was also considered and was included as a question in a feasibility assessment conducted by BioCryst. In addition, BioCryst sought expert advice from Key Opinion Leaders (KOLs) to define current use of prophylaxis medications in this HAE pediatric population. Those investigations found that the use of prophylaxis in the proposed study population was extremely limited due to numerous factors, one of which was lack of an orally administered option. That is, all approved options for the prophylaxis of HAE are injectables, which are more difficult and stressful to administer to children and none of which are approved for children below the age of 6 years. As a result, use of an active control group in this study was not considered feasible. Therefore, this study is designed as an open-label study with a 12-week standard-of-care (SOC) treatment period followed by a 12-week treatment period with berotralstat (Part 1). The SOC treatment period will serve as a control for safety assessments as well as provide additional data regarding baseline attack rates in this population.

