This is a single-arm, open-label study designed to evaluate the PK of berotralstat; plasma concentrations of berotralstat will be measured and used in population PK analyses, allowing for determination of the appropriate weight-based dose for pediatric patients 2 to < 12 years old. In addition, the safety and tolerability of berotralstat will be assessed when given to pediatric subjects who are 2 to < 12 years old as a prophylactic treatment to prevent attacks of HAE. The effectiveness of berotralstat in this population will be summarized using descriptive statistical methods. Subjects will be enrolled into 4 or more dose cohorts; subject weight will be used to determine assignment to each cohort with the higher weight cohorts (Cohorts 1 and 2) enrolling first and in parallel. Cohort 3 will open for enrollment and initiate the 12-week standard-of-care (SOC) phase after ≥ 4 subjects from Cohorts 1 and 2, with ≥ 2 of the subjects from Cohort 2, have reached Week 2. Cohort 4 will open for enrollment and initiate the 12-week SOC phase after ≥ 4 subjects in Cohort 3 have reached Week 2. BioCryst will notify sites when Cohorts 3 and 4 are open for enrollment. Safety assessments by the Data Monitoring Committee (DMC) and PK modelling from all available PK data to confirm the weight band for the cohorts will occur prior to dosing subjects in Cohorts 3 and 4 with berotralstat. Additional dose cohort(s) may be added if indicated based on safety and/or population PK analyses with DMC endorsement.

This study will consist of 2 treatment periods: a 12-week SOC treatment period followed by an open-label berotralstat treatment period lasting up to 144 weeks. The berotralstat treatment period is divided into 3 parts as defined below. Throughout the study, site personnel will monitor subject safety through a combination of in-person clinic visits and tele-communication with the parent/caregiver(s) (P/C). The tele-contact may be either a telephone call or telemedicine visit conducted over the internet.

SOC Treatment Period: Subjects will continue taking their SOC therapy for HAE (either short-term or long-term prophylaxis, or acute treatment for HAE attacks) for 12 weeks from the screening visit. No additional in-person visits are required during the SOC treatment period; however, at approximately 4 and 8 weeks following screening, site personnel will contact the P/C to assess AEs and the overall status of the subject.

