6.4. Data Presentation Conventions

Continuous data will be summarized using the number of subjects with available data, mean, standard deviation (SD) or standard error of the mean (SEM), median, minimum, and maximum. Categorical data will be summarized using counts/frequencies and percentages. Percentages will be calculated using the total number of subjects per cohort unless otherwise specified.

Means and medians will be formatted to 1 more decimal place than the measured value, SDs and SEMs to 2 more decimal places, and minimum and maximum values to the same number of decimal places. For categorical variables, the number and percentage of responses will be presented in the form XX (XX.X%) where the percentage is in the parentheses, except that 100% will be presented to 3 digits with no decimal. Adverse event data will be presented in the form XX (XX.X%) [XXX] where the number of subjects with at least 1 event (incidence) is the first number and the number of occurrences of an event is in “[]”. Dates will be formatted as DDMMYYYY and times will be formatted in 24-hour time as HH:MM. Partial dates will be handled as described in Section 8.5.

Berotrastat concentration data will be listed and summarized as part of the statistical analysis for this study and included in the Clinical Study Report. Noncompartmental PK parameters will be calculated as described in Section 10.1.2 and included in the Clinical Study Report. PK parameters from population PK modeling will be calculated and summarized as described in the Population PK Analysis Plan and included in the Population PK report.

Wherever possible, data will be decimal aligned.

A table of contents at the end of this SAP provides the expected titles and numbers of the tables, listings, and figures of the final report. Changes to titles or numbering in the final report will not necessitate a revision to the SAP, nor will they be considered deviations from planned analyses. Additional data listings supporting the tables will not be considered a deviation from planned analyses.

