6.7.4. Treatment-Emergent Adverse Events

TEAEs are defined as AEs that occurred on or after first dose of study treatment through 30 days post-discontinuation of study treatment. Additionally, it is assumed that an AE which was reported to have started on Day 1 without an associated onset time may have occurred after the initiation of berotralstat. Hence, AEs occurring on Day 1 with no associated onset time will be assumed to be treatment emergent.

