7. TREATMENT COMPARISONS

7.1. Data Display Treatment and Other Sub-Group Descriptors

Planned groups to be displayed on the summary tables are based on the cohort corresponding to initial dose as determined by subject weight/weight band at study baseline:

Cohort	Dose	Weight Band (at baseline)
1	150 mg capsule	≥40 kg
2	108 mg granules	32 to <40 kg
3	96 mg granules	24 to <32 kg
4	78 mg granules	12 to <24 kg
All Cohorts	All Doses	12 to ≥40 kg

Unless otherwise noted, tables will be arranged by cohort, and listings will be sorted by cohort, subject number, and date. Subjects will be analyzed by their original assigned cohort. Subjects who have their dose changed (decreased or increased) may be footnoted in Tables and Figures (eg, 1 subject in Cohort 1 had a dose decrease to xxx mg in Part x or Week xx). In addition, a listing of subjects with dose increases or decreases will be generated.

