- Any drug-related Grade 3 or Grade 4 TEAE
- Any TEAE leading to interruption of study drug (berotralstat)
- Any TEAE leading to discontinuation of study drug (berotralstat)
- Any TEAE leading to death.

TEAEs will be summarized by system organ class, PT, and cohort. TEAEs will also be summarized by system organ class, PT, severity, and cohort. TEAEs considered to be related to study drug will be summarized by system organ class, PT, and cohort. TESAEs will be summarized by system organ class, PT, and cohort. In addition, tables and listings of subjects who reported a TEAE with a preferred term that is included in the Hypersensitivity (narrow terms), Anaphylactic Reaction (narrow and broad terms) or Severe Cutaneous Reactions (narrow terms) standardized MedDRA queries (SMQs) will be generated. In addition, a table and listing will be generated for subjects who report either a TEAE with a preferred term that is included in the Torsade de Pointes (TdP)/QT prolongation SMQ or a TEAE with the preferred term Palpitation.

AEs, SAEs, and TEAEs considered to be related to study drug will be listed separately by treatment group, cohort, subject, and start date, showing system organ class, PT, and verbatim term.

An overall summary of AEs reported in the SOC period will be produced to summarize the overall number and percentage of subjects reporting:

- Any AE
- Any SAE
- Any drug related AE
- Any Grade 3 or Grade 4 AE
- Any AE leading to death.

A summary table of AEs reported in the SOC period will be presented overall by system organ class and PT. All AEs reported during the SOC will be listed.

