X	X		14.2.6.4	Summary of Average Number of Hospitalizations and Times Subject Sought Medical Care During Weeks 1-48	Week 48 Completer
X	X	X	14.3.1.1.1	Overall Summary of Treatment-emergent Adverse Events	Safety
X			14.3.1.1.2	Summary of Treatment-emergent Adverse Events, Part 1	Safety
X	X	X	14.3.1.2.	Subjects Reporting Treatment-emergent Adverse Events by MedDRA System Organ Class and Preferred Term	Safety
X	X	X	14.3.1.3	Subjects Reporting Treatment-emergent Adverse Events by MedDRA System Organ Class, Preferred Term, and Severity	Safety
X	X	X	14.3.1.4	Subjects Reporting Drug-related Treatment-emergent Adverse Events by MedDRA System Organ Class and Preferred Term	Safety
X	X	X	14.3.1.5.1	Subjects Reporting Serious Treatment-emergent Adverse Events by MedDRA System Organ Class and Preferred Term	Safety
X	X	X	14.3.1.5.2	Subjects Reporting Serious Treatment-emergent Adverse Events by MedDRA System Organ Class and Preferred Term, Part 1	Safety
X	X	X	14.3.1.5.3	Subjects Reporting Serious Treatment-emergent Adverse Events by MedDRA System Organ Class and Preferred Term, Part 1 and 2	Safety
X	X	X	14.3.1.6	Subjects Reporting Drug-related Serious Treatment-emergent Adverse Events by MedDRA System Organ Class and Preferred Term	Safety
X	X	X	14.3.1.7	Subjects Reporting Treatment-emergent Grade 3 or Grade 4 Adverse Events by MedDRA System Organ Class and Preferred Term	Safety

NDA IA	End of Part 2 (Wk 48) IA†	Final/ EOS**	Output Number	Title	Population
X	X	X	14.3.1.8	Subjects Reporting Drug-related Treatment-emergent Grade 3 or Grade 4 Adverse Events by MedDRA System Organ Class and Preferred Term	Safety
X	X	X	14.3.1.9	Subjects Reporting Treatment-emergent Adverse Events Leading to the Interruption of Study Drug by System Organ Class and Preferred Term	Safety
X	X	X	14.3.1.10	Subjects Reporting Treatment-emergent Adverse Events Leading to the Discontinuation of Study Drug by System Organ Class and Preferred Term	Safety
X	X	X	14.3.1.11	Most Frequently Reported Treatment-emergent Adverse Events	Safety
X	X	X	14.3.1.12	Subjects Reporting Special Situation Events	Safety
X	X	X	14.3.1.13.1	Subjects Reporting Treatment-emergent Adverse Events in the Hypersensitivity SMQ	Safety
X	X	X	14.3.1.13.2	Subjects Reporting Treatment-emergent Adverse Events in the Anaphylactic Reaction SMQ	Safety
X	X	X	14.3.1.13.3	Subjects Reporting Treatment-emergent Adverse Events in the Severe Cutaneous Adverse Reaction SMQ	Safety

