X	X	X	14.3.1.13.4	Subjects Reporting Treatment-emergent Adverse Events in the Hypersensitivity, Anaphylactic Reaction or Severe Cutaneous Reaction SMQs	Safety
X	X	X	14.3.1.14	Subjects Reporting Treatment-emergent Adverse Events in the Torsade de pointes/QTc Prolongation SMQ or Palpitation Preferred Term	Safety
X	X	X	14.3.1.15	Overall Summary of Adverse Events During the SOC Treatment Period	Safety
X	X	X	14.3.1.16	Subjects Reporting Adverse Events During the SOC Treatment Period by MedDRA System Organ Class and Preferred Term	Safety
X	X	X	14.3.4.1.1	Summary of Observed and Change from Baseline in Clinical Chemistry Laboratory Parameters	Safety
X	X	X	14.3.4.1.2	Summary of Observed and Change from Baseline in Hematology and Coagulation Laboratory Parameters	Safety
X	X	X	14.3.4.1.3	Summary of Observed and Change from Baseline in Quantitative Urinalysis Laboratory Parameters	Safety
X	X	X	14.3.4.2.1	Summary of Elevations in Post-Baseline Liver Function Tests	Safety
X	X	X	14.3.4.2.2	Hy's Law Plot of Maximum Total Bilirubin vs. Maximum ALT	Safety

NDA IA	End of Part 2 (Wk 48) IA†	Final/ EOS**	Output Number	Title	Population
X	X	X	14.3.4.2.3	Liver Test Safety Panel Over Time, Baseline vs. On-Study	Safety
X	X	X	14.3.4.2.4	Distribution of Liver Tests Over Time: ALT, AST, ALP, and Bilirubin	Safety
X	X	X	14.3.4.3	Treatment-Emergent Grade 3 and 4 Laboratory Toxicities by DAIDS Grades*	Safety
X	X	X	14.3.4.4.1	Shift from Baseline to Worst Post-baseline Assessment: Clinical Chemistry	Safety
X	X	X	14.3.4.4.2	Shift from Baseline to Worst Post-baseline Assessment: Hematology and Coagulation	Safety
X	X	X	14.3.4.4.3	Shift from Baseline to Worst Post-baseline Assessment: Urinalysis	Safety
X	X	X	14.3.5.1.1	Observed and Change from Baseline in 12-Lead ECG	Safety
X	X	X	14.3.5.1.2	12-Lead ECG Interpretation	Safety
X	X	X	14.3.5.1.3	12-Lead ECG QTcF Interval Categories	Safety
X	X	X	14.3.5.2.1	Observed and Change from Baseline in Vital Signs	Safety
X	X	X	14.3.5.3.1.1	Plot of Mean (SD) QTcF Observed Changes Relative to Baseline Over Time	Safety
X	X	X	14.3.5.3.1.2	Distribution Plots for QTcF Observed Changes Relative to Baseline Over Time	Safety
X	X	X	14.3.5.3.1.3	Distribution Plots for QTcF Observed Changes Relative to Baseline – All Observations	Safety
X	X	X	14.3.5.3.2.1	Plot of Mean (SD) PR Interval Observed Changes Relative to Baseline Over Time	Safety
X	X	X	14.3.5.3.2.2	Distribution Plots for PR Interval Observed Changes Relative to Baseline Over Time	Safety

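### For non-serious events, the Week 48 and final analyses list no 12-week berotralstat table to match the 12-week standard-of-care period that the protocol names as its safety control

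*SAP*

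**What the plan says.** On the role of the pre-treatment period, Protocol 4.4.4 states: "The SOC treatment period will serve as a control for safety assessments". The SAP synopsis describes "a 12-week SOC treatment period followed by an open-label berotralstat treatment period lasting up to 144 weeks".

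On what is counted, SAP 6.7.4 says: "TEAEs are defined as AEs that occurred on or after first dose of study treatment through 30 days post-discontinuation of study treatment". SAP 11.1 then says "TEAEs will be summarized by system organ class, PT, and cohort". The Week 48 analysis stops at the Week 48 visit (SAP 5.1), and the final analysis runs through Week 144 (SAP 5.2).

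On percentages, SAP 6.4 sets the default: "Percentages will be calculated using the total number of subjects per cohort unless otherwise specified". The same section shows adverse events as number of subjects, percentage and event count.

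The relevant outputs in SAP Table 7 (Section 14.1) are:

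- 14.3.1.15 and 14.3.1.16, adverse events in the standard-of-care period. The second is titled "Subjects Reporting Adverse Events During the SOC Treatment Period by MedDRA System Organ Class and Preferred Term". Both are marked for all three analyses.
- 14.3.1.2, TEAEs by system organ class and preferred term over all treatment time, marked for all three.
- 14.3.1.1.2, "Summary of Treatment-emergent Adverse Events, Part 1", marked for the NDA interim only.
- 14.3.1.5.2, serious TEAEs in Part 1 by system organ class and preferred term, marked for all three.

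Neither document specifies an adverse event rate per unit of exposure. The SAP does standardize other outcomes for time: attacks per 28 days (6.7.7.4), and hospitalizations and clinic visits divided by period length (6.7.7.13).

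**The concern.** In a single-arm study the standard-of-care period is the only internal reference for safety. A crude percentage of children with an event rises with the length of observation, whether or not the drug does anything. For a non-serious preferred term, the Week 48 and final analyses offer a 12-week figure before treatment and a 48- or 144-week figure on treatment, with nothing in between.

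This matters for the reactions already attributed to the drug in Protocol 4.4.5: reflux disease, diarrhea, vomiting and abdominal pain. Such events need not meet the seriousness criteria, so the matched table for serious events may not show them.

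A related, smaller point concerns by-visit percentages. SAP 11.5 gives QTcF categories by time point and names no denominator, so the SAP 6.4 default applies. Children may leave Part 3 for another source of drug. Read literally, a Week 144 percentage would then be divided by children who were no longer being examined.

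**Working it through.** **The plan's own figure.** Protocol 12.1 gives about a 96% chance of seeing at least one TEAE that occurs 10% of the time in 30 subjects. 1 − 0.9^30 = 0.958, so it reproduces. The statement does not say over what period the 10% applies.

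**Window lengths.** The standard-of-care period is 12 weeks. Treatment is 48 weeks at the end of Part 2 and up to 144 at the end of Part 3, so the ratios are 48/12 = 4 and 144/12 = 12. With the 30-day tail the longest window is 144 + 30/7 = 148.3 weeks, a ratio of 12.4.

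**Inflation with no drug effect.** Let p be the risk over 12 weeks. With constant hazard and every child followed throughout, the risk over T weeks is 1 − (1 − p)^(T/12). The documents give no value for p, so a range is shown. For p = 10%: 1 − 0.9^4 = 34.4% and 1 − 0.9^12 = 71.8%.

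| Assumed 12-week risk | Week 48 | Ratio | Week 144 | Ratio |
|---|---|---|---|---|
| 2% | 7.8% | 3.9 | 21.5% | 10.8 |
| 5% | 18.5% | 3.7 | 46.0% | 9.2 |
| 10% | 34.4% | 3.4 | 71.8% | 7.2 |
| 20% | 59.0% | 3.0 | 93.1% | 4.7 |
| 30% | 76.0% | 2.5 | 98.6% | 3.3 |
| 50% | 93.8% | 1.9 | 100.0% | 2.0 |
| 70% | 99.2% | 1.4 | 100.0% | 1.4 |

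The ratio is at least 3 only when p is below about 19% at Week 48 or about 33% at Week 144. A matched 12-week window, or a rate per patient-year, has an expected ratio of 1.00 in every row.

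**Sensitivity at p = 10%.**

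- Shorter follow-up: if every child were followed for 96 weeks, the figure is 1 − 0.9^8 = 57.0% (ratio 5.7); for 72 weeks, 1 − 0.9^6 = 46.9% (ratio 4.7).
- Heterogeneity: with gamma frailty of variance 2, H = (0.9^−2 − 1)/2 = 0.117. The risk is 1 − (1 + 2H × T/12)^(−1/2), which is 28.2% at Week 48 (ratio 2.8) and 48.8% at Week 144 (ratio 4.9).

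**By-visit denominator.** Take one child with a QTcF above a category limit at Week 144, out of 30 dosed. If 10 children had an ECG at that visit, the percentage is 1/10 = 10.0%; if 20 did, 1/20 = 5.0%. On the default denominator it is 1/30 = 3.3% either way. The attendance figures are assumptions. This illustration assumes early exits and the table above assumes none, so they are separate scenarios and cannot both describe the same late follow-up.

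**The case against.** Several stronger conclusions are tempting, and the documents do not support them.

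*That the plan itself contrasts 12 weeks with 144.* It does not. Protocol 12.2.5 has standard-of-care events summarized separately, the SAP gives them their own tables, and no hypothesis is tested. The mismatch arises only when a reader uses the control that the protocol offers.

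*That no matched table exists.* Serious events are matched at every analysis (14.3.1.5.2), and the NDA interim, which supports the submission, has a Part 1 summary of all TEAEs (14.3.1.1.2). That table's content is known only by its title, because the shells are a separate document (SAP 14.2); it may show more than the title suggests. Even so, it is not marked for the other two analyses.

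*That exposure is ignored.* Event counts accompany percentages (SAP 6.4) and duration of exposure is summarized (SAP 9.9), so a crude overall rate could be worked out. Those totals cannot isolate the first 12 weeks of treatment for a given non-serious preferred term; that would need the subject listings.

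*That an inert drug would always look several-fold worse.* For a common outcome, such as any adverse event, the percentage saturates and the ratio is 2 or less once the 12-week risk is 50% or more. The Week 144 figures also need full follow-up.

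*That dose-specific safety is mislabelled.* SAP 7.1 says "Subjects will be analyzed by their original assigned cohort" and labels the groups openly by initial dose and baseline weight. It provides for footnotes on dose changes, and the list of subjects with dose changes (16.2.5.2) is produced at every analysis. Grouping by starting dose does not cause the inflation; the column comparable with the standard-of-care table is the one for all cohorts.

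On denominators, the SAP 6.4 rule is only a default, and SAP 6.2 requires tables to show the number of subjects to which the data apply. After Week 48, ECGs are scheduled only at Week 144 and the end-of-study visit, so few displays are affected.

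**Conclusion.** The gap is real and specific. At the Week 48 and final analyses, non-serious TEAEs by preferred term have no 12-week counterpart to the standard-of-care table, and no adverse event rate per unit of exposure is specified at any analysis. For a preferred term with an assumed 12-week risk of 2% to 20%, an inert drug would show about 3 to 4 times the standard-of-care percentage at Week 48 and about 5 to 11 times at Week 144. This rests on constant hazard and complete follow-up, and it shrinks with early exits, heterogeneity or higher baseline risk.

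The by-visit denominator needs one clarifying sentence. It is an ambiguity of modest reach, mainly at Week 144.

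A matched window removes the difference in length but not every difference. The standard-of-care period requires only two remote contacts between screening and Day 1, whereas Part 1 has three clinic visits after Day 1 and one contact, so ascertainment may still be greater on treatment. The study is descriptive and conduct is unaffected. This should be corrected in the SAP before the later analyses, but it does not undermine the trial.

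**What to change.** In SAP Table 7, with matching text in SAP 11.1:

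1. Mark 14.3.1.1.2 for all three analyses. Add Part 1 TEAEs by system organ class and preferred term, in the layout of 14.3.1.15 and 14.3.1.16, with an all-cohorts column and the same Safety population.
2. Add events per patient-year for the standard-of-care period, Part 1, Parts 1 and 2 combined, and overall.
3. State in SAP 6.4 and 11.5 that by-visit categorical percentages use subjects with a non-missing assessment at that visit, and print that number.

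A display by dose at onset is optional.

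The cost is a few repeat-format tables and a sentence or two, from data already collected. The rates will be imprecise: if 30 children are dosed, Part 1 and the standard-of-care period each supply about 30 × 12/52 = 6.9 patient-years. They should be presented descriptively, beside the event counts.

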11.2. Exposure to Study Treatment and Treatment Compliance

The number of subjects exposed to study treatment and the number of subjects who discontinue treatment early will be presented on the disposition table. A summary of exposure to study treatment will also be presented. Listings of exposure to study treatment and of drug accountability will be provided by subject and treatment. Kaplan-Meier plots of duration of study

treatment (eg, time to discontinuation) will be provided. Subjects who discontinue study drug but continue to receive berotralstat via another mechanism will be considered completers.

Treatment compliance will be computed based on drug accountability by determining the number of capsules/packets taken relative to the number of capsules/packets that should have been administered.

For compliance (%) for the study period of interest based on the drug accountability page of the eCRF: *Number of Capsules or Packets Taken*

$$= \text{Number of Capsules or Packets Dispensed} - \text{Number of Capsules or Packets Returned} - \text{Number of Lost Capsules or Packets}$$

Expected Number of Tablets or Packets Taken

$$\begin{aligned} &= \sum_{i=1}^k (\text{CEILING}[\text{dose}_i \times (\text{Date of the Last Dose of Dose } i - \text{Date of the First Dose of Dose } i + 1)] - [\text{Interrupted}_i]) \\ &= (\text{CEILING}[\text{dose}_1 \times (\text{Date of the Last Dose of Dose } 1 - \text{Date of the First Dose of Dose } 1 + 1)] - [\text{Interrupted}_1]) \\ &\quad + \dots + (\text{CEILING}[\text{dose}_k \times (\text{Date of the Last Dose of Dose } k - \text{Date of the First Dose of Dose } k + 1)] - [\text{Interrupted}_k]) \end{aligned}$$

where i refers to the dosing period, dose_i is the per day dosing frequency for Period i , Interrupted_i is the number of dose interruptions for Period i , and k is the last period that dose changed. Subjects dose may change between visits; in this case the current dosing period will be split where the day before dose change will be the end of the prior period (and will retain the original frequency as specified at the start of the period) and a new period will begin the day of the change and dose_i will be adjusted to the new dosing frequency based on the case report form (CRF) specified frequency change. In the event a subject has not taken a dose on date of change or interruption (as specified in the CRF) and the frequency changed from a daily regimen ('Once daily' or '2 packets daily') to 'Every other day', the prior dosing period will end the date before the date of change and the new dosing period will begin the day following the date of dose change. In the case of missing interruptions for a given period, the number of dose interruptions for that period will be imputed as zero. In the case of missing values for number of capsules or packets returned or number of lost capsules or packets for a given period, data for that dosing period will be considered missing and will be excluded in the calculation of compliance.

Treatment compliance based on dispensing information will be calculated for each study treatment that the subject received as follows:

$$\text{Treatment Compliance (Dispensed)} = \frac{\text{Number of Capsules or Packets Taken}}{\text{Expected Number of Capsules or Packets Taken}} \times 100$$

Treatment compliance will be listed and summarized for Part 1, defined as Day 1 to Week 12; Part 2, defined as Week 13 to 48; and overall.

A categorical summary of treatment compliance will be produced with the following categories shown in Table 6.

Table 6: Definition of Compliance Categories

Compliance	Range of Compliance (%)
Poor compliance	<80%
Acceptable compliance	80% – <90%
Good compliance	90% – 110%
Over-dosing	> 110%

Treatment compliance will also be calculated between scheduled visits (or between the final dispense date and the final return date) like above with the following changes for Part 1 only. The expected number of capsules or packets will be computed as the number of capsules or packets expected between scheduled dispense dates. Drug will be assumed to have been taken during the period after the drug was dispensed, if the bottle or empty packet is returned, regardless of the return date. Visits for which no bottles or empty packets are returned at any time are considered missing data and compliance is not calculated in these cases. Note that this calculation does not consider any protocol allowable study drug interruptions.

